## BACKGROUND

### *Study Purpose and Rationale*

This research is designed to remedy unaddressed and interlocking HIV-prevention and mental health needs among gay, bisexual, and other men who have sex with men (GBMSM) in the Central Eastern European country of Romania, and their underpinning stigma-related mechanisms. Rampant stigma contributes to the increasing prevalence of HIV among Romanian GBMSM (from under 10% in 2009 to close to 20% in 2014, by best available estimates) and keeps GBMSM out-of-reach of HIV prevention services. The team's mHealth pilot intervention (titled "Comunica: Despre Mine. Despre Noi." [COMUNICA] translated as "About Me. About Us."), which reduced US and Romanian GBMSM's risk for HIV infection while also reducing depression and alcohol abuse in initial pre-post trials, is now ready for testing in a randomized controlled trial with a large national sample in the current study. The Comunica intervention entails eight 60-minute live chat sessions delivered by trained counselors on our mobile study platform using motivational interviewing (MI) and cognitive-behavioral skills training (CBST).

First, during pre-trial (months 1-5), in collaboration with a community advisory board consisting of GBMSM community members, GBMSM-affirmative physical and mental health providers, and a technical developer, the team fine-tuned the Comunica intervention based on pilot findings and evaluation interviews, and expand the original Comunica education materials for an education attention condition that will serve as a control arm.

Second, during the intervention phase (months 6-45), the team will recruit, screen, assess, and randomize GBMSM at risk for HIV infection and alcohol abuse to either the Comunica intervention (n=163) or education attention condition (n=163). The conditions are content matched, and both are hosted on the study platform. While Comunica will consist of eight weekly mHealth live chat sessions, the education attention control condition will consist of eight self-administered educational modules.

Third, during the follow-up phase (months 8-55), the team will assess at 4, 8, and 12 months post-baseline, in a mobile fashion identical to the baseline, the primary outcome of condomless anal sex (CAS) with male partners, secondary outcomes of alcohol abuse, depression, and anxiety, and psychosocial mechanisms rooted in the Information-Motivation-Behavioral Skills (IMB)

model (e.g., HIV/STI knowledge, condom use self-efficacy) and minority stress theory (e.g., identity concealment, internalized homophobia).

### *Research Aims & Abstracts*

Aim 1. Test the relative efficacy of the Comunica mHealth intervention compared to a content-matched education attention control condition in changing (a) the primary outcome: CAS with HIV-positive or unknown-status partners and (b) secondary outcomes: depression, anxiety, and alcohol abuse. Outcomes are measured at preintervention (baseline), and at 4-, 8-, and 12-month follow-ups.

Primary and Secondary Outcomes (Aim 1). Comunica GBMSM, compared to education attention control condition GBMSM, will report significantly greater changes on primary (decreased CAS) and secondary (decreased alcohol use, depressive symptoms, and anxiety symptoms) outcomes across 12 months.

Aim 2. Test motivational and stigma-related mechanisms of intervention efficacy. Hypothesized motivational mechanisms include HIV/STI and alcohol-related knowledge and behavioral skills as well as condom-use and refraining-from-alcohol-use self-efficacy, grounded in the IMB model. Hypothesized minority stress mechanisms include collective self-esteem, internalized homophobia, identity concealment, and stigma consciousness, which are grounded in minority stress theory and are particularly relevant for GBMSM in high-stigma countries.

IMB and Minority Stress Mediation Hypothesis (Aim 2). Comunica GBMSM, compared to education attention condition GBMSM, will report greater improvement in 1) knowledge of sexual health and deleterious effects of alcohol use, 2) motivation to change risk behavior and 3) behavioral self-efficacy to execute changes across 12 months. Comunica GBMSM, compared to education attention condition GBMSM, will also report significantly greater shifts in minority stress (e.g., attenuated internalized homophobia, identity concealment) across 12 months. Improvements in IMB and minority stress mechanisms will precede and statistically mediate intervention effects, based on our conceptual model.

## STUDY DESIGN

First, in a pre-trial phase (months 1-5), in collaboration with a community advisory board (CAB) consisting of collaborators, gay and bisexual men, gay and bisexual men-affirmative physical and mental health providers, and technical developer, we will first fine-tune and pre-test the Comunica intervention based on pilot findings and exit interviews, and expand the preliminary education materials for the education attention control condition.

Second, during the intervention phase (months 6-45), the team will recruit, screen, assess, and randomize gay and bisexual men at risk for HIV infection, alcohol abuse, and depression to either the Comunica intervention (n=163) or education attention condition (n=163). The conditions are content matched, and both are hosted on the study platform. Comunica consists of eight weekly mHealth live chat sessions; education attention condition will consist of eight self-administered educational modules.

### *Eligibility*

Potential participants will be eligible if they report:

- 1) Male sex at birth and current male identity
- 2) Age 16 years and above
- 3) At least 1 CAS act with an HIV-positive or status-unknown male partner in the prior month
- 4) At least 1 heavy drinking day in the prior month
- 5) Own a mobile device (e.g., smartphone, tablet, laptop)
- 6) Planned residence in Romania for the duration of study participation (12 months)
- 7) Not currently using HIV pre-exposure prophylaxis (PrEP)
- 8) Confirmed to be HIV-negative upon testing at baseline

### *Baseline (BL), 4-, 8-, and 12-month Assessments*

The project coordinator will send a link to the BL survey to all HIV-negative participants, and tell them that they will be contacted by their counselor after submitting the survey. The quarterly self-administered mobile assessments are identical, take 45 minutes to complete, have been validated by the Romanian pilot gay and bisexual men participants, and assess: 1) sexual

behavior (e.g., number of CAS acts; number and types of partners; sex under the influence) and 2) past-3-month alcohol use; 3) depressive symptoms; 4) HIV/STI testing and other healthcare access (e.g., annual exams; mental health) patterns; 5) hypothesized mediators of intervention efficacy, including IMB model components (e.g., HIV-risk-related information, motivation, behavioral skills) and minority stress (e.g., outness, internalized homonegativity, collective self-worth); and 6) demographics and psychosocial risk contexts, including intimate partner violence. Third, during the follow-up phase (mos 8-55), we will assess at 4, 8, and 12-mos post-baseline, in the same web-based fashion as at baseline, the primary outcome of CAS with male partners, and secondary outcomes of alcohol abuse, depression, anxiety, and psychosocial mechanisms rooted in the Information-Motivation-Behavioral Skills (IMB) model (e.g., HIV/STI knowledge, condom use self-efficacy) and minority stress theory (e.g., identity concealment, stigma consciousness).

We hypothesize that 1) compared to gay and bisexual men in the education attention control arm, those randomized to the Comunica arm will report significant reductions in CAS acts, depression symptoms, and anxiety symptoms across the 12-month follow-up, 2) IMB and minority stress mechanisms will statistically mediate intervention efficacy, and 3) compared to the control condition, the Comunica intervention will prove cost-effective in terms of reducing depression, anxiety, and alcohol abuse.

#### *Intervention Content*

Comunica Content. The intervention aims to support gay and bisexual men in reducing their CAS act and alcohol use and improving their mental health. Comunica is delivered over eight 60-min live chat sessions on our mHealth study platform compatible with any mobile device (e.g., laptops, smartphones).

Theoretical Grounding. Comunica is based on the IMB model of health behavior change, which postulates that individuals must possess the requisite information on sexual health and alcohol, motivation to change their HIV risk and alcohol use, and behavioral skills self-efficacy to reduce their risk. Therefore, Comunica includes MI to provide accurate information about HIV transmission, alcohol abuse, and local GBMSM-affirmative health resources (e.g., HIV-testing sites) and build motivation to improve behavioral skills (via CBST). MI is an evidence-based form of person-centered therapeutic communication that privileges client values and preferences for change to help individuals resolve ambivalence and move toward their valued goals. Skills-

building is often a natural outcome of MI, especially for individuals who attain a high degree of motivation for change. CBST is a therapeutic approach used in the treatment of various behavioral problems, such as alcohol abuse, depression, and more recently high HIV risk. CBST can help modify cognitions driving unhealthy behaviors, promote awareness of contextual triggers and unhealthy behavioral patterns, and teach coping skills to improve health. Comunica also draws upon minority stress theory recognizing that stigmatizing societal contexts compromise health behavior. GBMSM in highly stigmatizing contexts such as Romania experience a lack of structural protections (e.g., national policies), institutional support (e.g., GBMSM-affirmative healthcare), and coping resources (e.g., social support). Thus, the CBST skills in Comunica are presented in a manner that acknowledges the barriers that social stigma poses to GBMSM's health, while empowering them to circumvent these barriers by building self-efficacy, effective communication, and planful problem-solving. Safety protocols include instructions for protecting participants' identities, data, and safety.

Education Attention Control Condition. The control condition consists of eight modularized topics content-matched with the Comunica sessions, which we have generated based on the team's HIV-prevention education with GBMSM in the US and Romania. Topics include 1) GBMSM identity, 2) "HIV 101," 3) HIV/STI testing, 4) alcohol and the body, 5) the role of alcohol in HIV risk, 6) HIV-status disclosure and sexual health communication, 7) finding social supports, and 8) a summary. To maintain uniformity of information exposure across participants and maximize learning, each screen will be timed at a comfortable speed and participants will be unable to advance to the next screen prior to the set time limit. Control participants will receive five quiz questions after each module, with correct answers on a subsequent screen.

**Building Mobile HIV Prevention and Mental Health Support in Low-resource
Settings**

NCT #: NCT03912753

July 8, 2024

Statistical Analysis Plan

Introduction

The current study aims to test the efficacy of Comunică, a motivational interviewing intervention also informed by minority stress theory, to reduce HIV-transmission-risk behavior in a randomized controlled trial among Romanian gay and bisexual men (GBM). In this study, the primary outcome involves HIV-transmission-risk behavior. Secondary outcomes include depression, anxiety, heavy alcohol use, and suicidality. Exploratory outcomes include HIV and STI (chlamydia, gonorrhea, syphilis) diagnosis and HIV/STI testing patterns. The control condition, referred to as “educational attention control (EAC)” consists of eight educational modules that present information regarding GBM’s identity development, HIV/STI prevention, heavy alcohol use and its associations with HIV-transmission-risk behavior, sexual health communication, and the importance of social support. This EAC was created in consultation with Romanian GBM community members and advocates.

Study Design

In this RCT, Comunică is compared to EAC to examine relative change in: (a) the primary outcome, HIV-transmission-risk behavior defined as: frequency of condomless anal sex acts with HIV-positive or unknown-status partners outside of the context of one’s own adherent PrEP use or only with a primary partner that has adherent PrEP use or has undetectable viral load and (b) secondary outcomes: depression, anxiety, heavy alcohol use, and suicidality. Sessions for both conditions are to be completed over the course of four months. Outcomes are measured by self-report at pre-intervention (baseline), and at 4-, 8-, and 12-month follow-ups. At baseline and 12-month follow-up, all participants also self-administer at-home rapid testing for HIV and syphilis, and self-collect sampling (urethral, pharyngeal, rectal) for chlamydia and gonorrhea, which are sent to a laboratory for analyses.

Table 1. Primary and Secondary Outcome Measures

Domain	Measure (1°, 2°)	Source, Frequency, and Sample
HIV-risk behavior	HIV-transmission-risk behavior (1°)	Condomless anal sex acts with HIV-positive or unknown-status partners outside of the context of one’s own adherent PrEP use or only with a primary partner that has adherent PrEP use or has undetectable viral load. This is measured with an online self-administered Timeline Follow-Back (TLFB) instrument. The TLFB yields past-30-day incidence of HIV risk behavior in terms of type of sexual behavior, condom use, partner(s) HIV status, self and partner adherent PrEP use (at least 4 days per week), sex while using drugs or alcohol, and number of sexual partners. HIV risk behavior acts as defined above will be measured as the pooled number (count) over 30 days prior to the 4-, 8-, and 12-month follow-up visits. A primary supportive analysis of this outcome will assess the above as any such behavior (binary) during the 30 days prior to the 4-, 8- and 12-month follow-up visits.
Mental health and substance use	Depression (2°)	Center for Epidemiologic Studies Depression Scale (CES-D) (continuous) at 4-, 8-, and 12-month follow-up visits and using cutoff ≥ 16 (binary) at 4-, 8-, and 12-month follow-up
	Anxiety (2°)	Beck Anxiety Inventory (BAI) (continuous) at 4-, 8-, and 12-month follow-up visits and using cutoff ≥ 16 (binary) at 4-, 8-, and 12-month follow-up

	Heavy alcohol use (2°)	Alcohol Use Disorders Identification Test (AUDIT-C) (continuous) at 4-, 8-, and 12-month follow-up and using cutoff ≥ 4 (binary) at 4-, 8-, and 12-month follow-up; Percentage of TLFB-Heavy Drinking Days in the previous 30 days
	Suicidality (2°)	Suicidal Ideation Attributes Scale (SIDAS) (continuous) at 4-, 8-, and 12-month follow-up and using cutoffs ≥ 21 (binary) at 4-, 8-, and 12-month follow-up

Table 2. Exploratory Outcome Measures

Domain	Measure	Source, Frequency, and Sample
HIV-risk behavior	HIV/STI testing	HIV/STI testing (any/none) (besides study-administered testing) over 12 months
	HIV and STI diagnosis	HIV and STI self-reported testing (gonorrhea; chlamydia; syphilis) (besides study-administered testing) over 12 months

Sample size

The primary and secondary outcome measures are summarized in Table 1.

The Comunică study originally proposed to recruit 326 subjects. This was based on calculations that the study would have 80% power to detect effect sizes ranging from 0.25 to 0.27 if the study attained 80% retention of the study subjects. However, recruitment was slower than planned (due to the COVID-19 pandemic and likely other factors), although retention was better than the 80% estimated.

Therefore, as we approached the end of recruitment for the Comunică study, three factors that were not available when we wrote the proposal transpired: i) While 303 participants were finally enrolled, we had re-estimated that we would likely only be able to recruit 288 subjects by 31 December 2022 (our date of termination of recruitment) and based power re-estimation on this number. ii) The overall participation rate for attending all three post-intervention visits was 86% (with a high proportion of the remaining sample completing 2 post-interventions assessments). iii) From preliminary analysis of our data, we had normative distributions of the study outcomes that could be used in establishing a study design and metrics for powering the primary outcome. To that end, we re-estimated the study power as described below and this new estimate was approved by the Data Safety and Monitoring Board (DSMB).

In the original proposal, a repeated measures mixed linear model (or generalized estimation equation) using all 4 study visits (Baseline, and 4-, 8-, and 12-month follow-ups) was planned. However, the distribution of our primary outcomes (HIV-transmission-risk behavior) based on the data we now had near the end of the study was problematic for fitting this type of model, which is based on a central limit theorem assumption that may not manifest. Namely, there were two issues to consider: 1) at each follow up visit, over 50% of participants manifest no HIV-transmission-risk behavior creating a large point mass at the lower limit of 0. 2) On the other end, the distribution of HIV-transmission-risk behavior acts was very skewed with numbers of acts greater than 50 leading to skewness much > 3 , which again contradicts normality-based methods.

Importantly for power estimation, the correlation of baseline and the average 12-month HIV-transmission-risk behavior acts was 0.37, which means that after adjustment for the pre-intervention behavior, the standard deviation of the post-intervention behavior would be the square root of $(1-0.37^2) = 0.93$ that of the unadjusted outcome. Based on this and with 288 subjects, 86% of whom participated in all 3 visits as we have been observing will happen (or conservatively 123 in each treatment arm), there is 80% power to detect an effect size of 0.33, slightly greater than our originally estimated effect size of 0.25-0.27 and at the upper end of the range of effect sizes found for behavioral interventions addressing multiple health outcomes among sexual minority men (Pantalone et al., 2020). We believe that 0.33 represents a plausible effect size to detect in this trial given the strong distinction between the two intervention conditions, with one involving an active therapist-guided intervention and the other consisting of self-guided psychoeducation only. The standard deviation of the (Winsorized)

averaged outcome over 12 months per-assessment HIV-transmission-risk behavior acts was 3.46 acts. Multiplying this standard deviation by the effect size of 0.33 gives 1.14 HIV-transmission-risk behavior acts. This means that the study will have 80% power to detect an overall mean reduction of 1.14 HIV-transmission-risk behavior acts in the prior 30 days per assessment period in the intervention compared to the control condition.

It should be noted that our final analysis will most likely incorporate the partial information from men with only 1 and 2 post-intervention follow-up visits through imputations or more exactly adjustment of the partial information for number of trimesters reported. If so, this would increase power, by a very modest amount.

DRAFT ANALYTIC PLAN FOR COMUNICĂ STUDY

1. Overview

The analysis of the primary and secondary outcomes will use intent-to-treat with participants analyzed according to their original treatment assignment. SAS 9.4, SPSS 26.0, Stata and/or R software will be used for all analyses.

2. Comparability of Treatment Groups

Differences in baseline demographic characteristics between the two treatment arms will be assessed using appropriate graphical and statistical methods including summary statistics and p -values from exact, rank, chi-square, t -tests and ANOVA. Of note, later on in the analysis, we will control for variables related to the study outcome in the analyses. We will also investigate if the randomization scheme was compromised.

3. Analysis of Primary Outcome: Number of condomless anal sex acts in the past 30 days with HIV-positive or unknown-status partners outside of the context of one's own adherent PrEP use or primary partner's adherent PrEP use or undetectable viral load in the past 30 days (HIV-transmission-risk behavior)

The statistical significance threshold for an intervention (vs. control) arm effect will be a two-sided $p \leq 0.05$. The primary outcome will be evaluated between the treatment arms at 4-, 8-, and 12-month follow-ups combined in a repeated measures analysis that adjusts for baseline behavior. This will be analyzed using negative binomial regression with baseline, and 4-, 8-, and 12-month follow-ups clustered within the same person. Main effect terms for 4-, 8-, and 12-month follow-ups post-baseline (each timepoint vs. baseline) will be included in the model. A single interaction term between the 4-, 8-, and 12-month measures with the intervention arm will be included in the model to test for pooled post-baseline treatment arm differences. The relative number of HIV-transmission-risk behavior acts with a 95% confidence interval about this term will quantify intervention effect. Generalized estimating equations with person as the cluster will be used to account for within person repeated measure collinearity. As a sensitivity analysis, this will be repeated including all baseline covariates that are statistically associated ($p < 0.05$ to enter and $p \geq 0.10$ to leave in a stepwise selection) with HIV-transmission-risk behavior in negative binomial GEE models with person as the cluster and adjusting for time of visit (i.e. 4-, 8-, and 12 months each vs. baseline).

If there are excess zeros at each post-baseline visit, we will consider using a zero-inflated negative binomial model instead. However, this approach will split the intervention effect

parameter into two models and thus may dampen power to detect statistical significance for an intervention that affects both parts. In this setting, we thus will more likely use the sensitivity analysis approach described below.

Other Sensitivity Analyses: As a sensitivity analysis, averaged HIV-transmission-risk behavior over all 3 post-baseline visits (or 2 post-baseline visits if one visit is missing) will be used as the outcome in an ANCOVA linear regression model that adjusts for baseline HIV-transmission-risk behavior as a predictor and includes treatment arm assignment as a covariate. For those who are missing one post-baseline visit, indicator variables as to which visit is missing will be included. The mean difference in HIV-transmission-risk behavior acts with a 95% confidence interval about this term will quantify intervention effect. This will be repeated including all baseline covariates that are statistically associated ($p < 0.05$) with HIV-transmission-risk behavior in Stepwise selection ($p < 0.05$ to enter and $p \geq 0.10$ to leave) into the above model. Should the negative binomial model described in the first paragraph of section 3. fail to converge, this will become the primary analysis. The statistical significance threshold for the new (vs. control) intervention arm effect will again be a two-sided $p \leq 0.05$.

4 Analysis of Secondary Outcomes

The Secondary Outcomes of interest (all of these taken pre-intervention and at 4-, 8-, and 12-month follow-ups) are:

- Depression as measured by The Center for Epidemiological Studies-Depression Scale (CES-D). CES-D will be examined as a continuous variable and as a binary variable using the cutoff of ≥ 16 (indicating clinical depression).
- Anxiety as measured by Beck Anxiety Inventory (BAI). BAI will be examined as a continuous variable and using the cutoff of ≥ 16 (indicating potentially concerning levels of anxiety).
- Suicidality as measured by Suicidal Ideation Attributes Scale (SIDAS). SIDAS will be examined as a continuous variable and as a binary outcome using the cutoff of ≥ 21 (indicating high risk of suicidality) as well as any score above 0.
- Alcohol consumption as measured by
 - The Alcohol Use Disorders Identification Test (AUDIT-C). AUDIT-C will be examined as a continuous variable and as a binary outcome using the cutoff of ≥ 4 .
 - Percentage of Heavy drinking Days in the past 30 days prior to the visit will be examined as a continuous variable.

Due to multiple comparison issues, these will each be tested individually using a two-sided Type-1 error of 0.01 and quantified using 99% confidence intervals.

Levels of these measures at 4-, 8-, and 12-month follow-up will be compared (adjusting for the level at the baseline visit) between the Comunică intervention and EAC group in repeated measures analyses as described below.

4-A For Continuous Outcomes that are Heavily Skewed to the Right and Without an Excessive Point Mass at 0 for 4-, 8-, and 12-months follow-up

We anticipate that BAI and number of heavy drinking days will fall into this category. A similar approach to that described for the Primary Outcome will be used.

4-B For Continuous Outcomes that are not Heavily Skewed to the Right at 4-, 8-, and 12-months follow-up

We anticipate that CES-D and AUDIT-C will fall into this category. We will fit repeated measure linear regression mixed models for outcomes at baseline and 4-, 8-, and 12-months follow-up with subject intercept as a fixed effect, main effects for 4-, 8-, and 12-months and a single interaction term between treatment arm assignment and the timepoint being post intervention delivery. In sensitivity analyses, this will be repeated including all baseline covariates that are statistically associated ($p < 0.05$) with the outcome in univariate models using stepwise selection ($p < 0.05$ to enter $p \geq 0.10$ to leave) into the above-described models. The mean post intervention difference in the outcome between the treatment arms with 95% confidence intervals about this term will quantify intervention effect.

4-C For Binary Outcomes

We will also look at the following binary outcomes: HIV-transmission-risk behavior > 0 , CES-D ≥ 16 , SIDAS ≥ 21 , SIDAS ≥ 0 , AUDIT-C ≥ 4 in repeated measures model using the post-baseline visit and post intervention visits at 4-, 8-, and 12-month follow-ups. Repeated measures generalized estimation equations will be fit about individual as the cluster using a logit link. The visit number (i.e., 4-, 8-, and 12-months vs. vs. baseline) and treatment arm assignment will be included as main effects, as will the baseline preintervention level of the outcome being modeled. In sensitivity analyses, this will be repeated including all baseline covariates that are statistically associated ($p < 0.05$) with the outcome using Stepwise selection ($p < 0.05$ to enter $p \geq 0.10$ to leave) into the above-described models. The intervention effect will be quantified by Odds Ratios with 95% confidence intervals.

We will also use exact tests to compare treatment arms for having been ever diagnosed during the single timepoint 12-month study follow up with HIV, syphilis, chlamydia, and gonorrhea.

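### Comunica is delivered by counselors and control is self-administered, but no planned model has a counselor term; if outcomes differ between counselors, the arm-effect standard error is too small

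*SAP*

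**What the plan says.** **Delivery.** The Protocol (Study Purpose and Rationale) describes Comunica as "eight 60-minute live chat sessions delivered by trained counselors on our mobile study platform". For control, the Protocol (Study Design) says the "education attention condition will consist of eight self-administered educational modules". The SAP's sample size section relies on this contrast to justify the effect size of 0.33: "with one involving an active therapist-guided intervention and the other consisting of self-guided psychoeducation only".

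**Analysis.** SAP section 3 fits a negative binomial model to baseline and the three follow-ups: "Generalized estimating equations with person as the cluster will be used to account for within person repeated measure collinearity". The covariate-adjusted repeat also clusters on person. The ANCOVA in section 3, which becomes primary if the negative binomial model does not converge, has no counselor term. Neither do the linear mixed models in section 4-B or the binary GEEs in section 4-C. The linear model behind the power calculation has a single error term with constant variance.

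**Not stated.** The documents do not give the number of counselors, their caseloads, how men are assigned to them, an ICC, or a sensitivity analysis for counselor effects.

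**A complication.** In the Protocol's section on baseline and follow-up assessments, the survey link goes to all HIV-negative participants, and the coordinator is to "tell them that they will be contacted by their counselor after submitting the survey". That sentence is not limited to Comunica men.

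**The concern.** This is a partially nested design: one arm is grouped by the person who delivers treatment and the other is not. Eight hours of live contact is the main difference between the arms, so differences between counselors are a plausible source of variation in outcome. Randomization does not remove this, because the correlation arises afterwards, through delivery, and in one arm only.

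The planned variance treats men as independent. If men with the same counselor have positively correlated outcomes, the variance of the Comunica arm's result is understated. The confidence interval is then too narrow, and the tests run above their nominal level (0.05 for the primary outcome, 0.01 for secondaries). Power is 80% only for an effect that the SAP itself puts at the upper end of the published range, so a borderline result is realistic and a modest understatement could decide it.

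**Working it through.** **Inputs from the SAP, sample size section.** 123 evaluable men per arm; baseline correlation 0.37; effect size 0.33; SD 3.46 acts; two-sided alpha 0.05; stated power 80%.

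**Assumed, because the documents do not give them.** Number of counselors K, counselor ICC, and equal caseloads. Normal approximation throughout.

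**Step 1: reproduce the stated power with independent men.**
- Residual SD factor = √(1 − 0.37²) = 0.929.
- SE of the difference in SD units = 0.929 × √(2/123) = 0.1185.
- Power = Φ(0.33/0.1185 − 1.96) = Φ(0.826) = 79.5%.
- 0.33 × 3.46 = 1.14 acts.

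The 80% is reproduced, but only if all men are independent.

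**Step 2: allow for counselors in Comunica only.**
- Men per counselor: m = 123/K.
- Design effect in Comunica: D = 1 + (m − 1) × ICC. In control it is 1.
- True SE divided by planned SE: r = √((1 + D)/2).
- Actual type I error of a nominal 5% test: 2 × [1 − Φ(1.96/r)].
- Power with a correct SE, for an effect nominally at 80%: Φ(2.80/r − 1.96).

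| K | ICC | m | D | r | Type I error | Power |
|---|---|---|---|---|---|---|
| any | 0 | – | 1 | 1 | 5.0% | 80% |
| 15 | 0.01 | 8.2 | 1.072 | 1.018 | 5.4% | 79% |
| 10 | 0.02 | 12.3 | 1.226 | 1.055 | 6.3% | 76% |
| 6 | 0.05 | 20.5 | 1.975 | 1.220 | 10.8% | 63% |

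For the last row: D = 1 + 19.5 × 0.05 = 1.975; r = √(2.975/2) = 1.220; 1.96/1.220 = 1.607, which gives 10.8%; 2.80/1.220 − 1.96 = 0.336, which gives 63%. A true SE 1.22 times the planned one means that the planned SE is 1 − 1/1.22 = 18% too small. The effect detectable with 80% power becomes 0.33 × 1.22 = 0.40, or about 1.39 acts instead of 1.14.

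**Step 3: secondary outcomes at 0.01.** Replacing 1.96 by 2.576 in the type I error formula gives 1.1%, 1.5% and 3.5% for the three cases.

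**Step 4: check the direction in the planned type of model.** A simulation used a negative binomial working variance, independence working correlation and a person-level sandwich, with 123 men per arm, four visits, 2,000 runs per setting and assumed mean and dispersion. With 6 counselors and a counselor SD of 0, 0.2, 0.3 and 0.4 on the log scale, null rejection was 6.7%, 7.5%, 11.0% and 13.4%. With 10 counselors it was 7.0%, 8.2%, 8.5% and 11.7%. The excess over 5% at SD 0 is small-sample sandwich bias and has nothing to do with counselors. The rise from that level is the counselor effect.

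**The case against.** **The size rests on assumption.** This stands. A reader might infer that the trial's type I error exceeds 0.05 and that its power is below 80%. The documents do not support that as a fact. They give no counselor count, caseload or ICC, and the range above runs from trivial to serious purely by choice of inputs. The largest case combines the fewest counselors with the highest ICC.

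**Who has a counselor is not fully clear.** This stands in part. A reader might infer that each Comunica man has one assigned counselor and that control men have no contact with any. The only text on a man's own counselor is the baseline instruction, "they will be contacted by their counselor after submitting the survey", and it covers all HIV-negative participants, including men who will be in control. That Comunica men share counselors is also inferred: 163 planned men with eight live sessions each make one counselor per man implausible, but sharing is not stated. A brief contact with control men would not remove the difference in delivery, which both documents describe plainly.

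**Person-only standard errors can be defended.** They are valid if inference is limited to the particular counselors in this trial. The SAP does not say that it is.

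**A counselor random intercept would not repair section 4-B.** This also stands. Those models include baseline as an outcome and give each subject an intercept. A counselor intercept that is constant over time is absorbed by it and leaves the standard error of the arm-by-post-intervention term unchanged. The remedy has to be placed on the post-intervention term.

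**Conclusion.** The point holds in conditional form. Treatment is counselor-delivered in one arm only, every planned model and the power calculation treat men as independent, and a person-level sandwich does not repair that. If counselors differ in their results, the planned standard error is too small.

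Under the assumed cases on 123 men per arm, nominal 5% tests run at 5.4% to 10.8%, and power with correct standard errors is about 79% to 63%. These figures assume equal caseloads and a normal approximation. With few counselors, t-based degrees of freedom would lower power further. With ICC 0 there is no effect, and with many counselors and ICC 0.01 it is small. The change is worth making because it protects the error rate and shows readers whether the result depends on assuming independence.

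**What to change.** 1. **Negative binomial GEE, binary GEEs and ANCOVA.** Keep the mean model. With an independence working correlation in the GEEs, the point estimate also stays the same. Compute the sandwich variance with counselor as the cluster in Comunica and each control man as his own cluster, with a small-sample correction. If there are very few counselors, pre-specify this as a sensitivity analysis.
2. **Linear mixed models (section 4-B).** Put a counselor random effect on the Comunica post-intervention term, not on a time-constant intercept, and use Satterthwaite or Kenward-Roger degrees of freedom.
3. **Reporting.** Give the number of counselors, their caseloads and the estimated ICC. State whether inference is meant to extend beyond these counselors.
4. **Clarification.** State who contacts control men after the baseline survey, and reconcile that instruction with the description of control as self-administered.

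**Cost.** SAP wording and some programming; no new participants or visits. Intervals will be wider and degrees of freedom fewer, which may be material if counselors are few. The change also requires that the counselor for each Comunica man was recorded, which the documents do not state.
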